As part of the pilot RCT, we also gathered serial serum venous blood samples from a subset of participants. This was done for two main purposes: 1) to ensure a reliable but safe rise in ionized calcium from the 1-gram dose of CaCl₂, and 2) to generate sample size calculations for a definitive study of CaCl₂ PK in a similar pregnant patient cohort. Data and a 1-compartment PK model are shown in **Figure 1**. As anticipated, a rapid and reliable and safe-level peak in ionized calcium was obtained in subjects who received CaCl₂.

EXPERIMENTAL DESIGN AND METHODS

SPECIFIC AIM 1 OVERVIEW: Based on our preliminary data, we propose a double-blind, placebo-controlled, 120-patient RCT to assess the effect of prophylactic CaCl₂ infusion upon blood loss and uterine tone at the time of intrapartum cesarean delivery. Patients will be randomly assigned to receive a prophylactic infusion containing one gram of dilute CaCl₂ or saline placebo in addition to standard of care oxytocin after fetal delivery. We will assess quantitative blood loss and serial measurements of uterine tone.

Study population: The study will enroll adult pregnant patients age 18-45 years of age at >34 weeks gestation who require intrapartum cesarean delivery and have received an exogenous oxytocin infusion for labor induction or augmentation, as these are known risk factors for uterine atony^{1,2}. Exclusions include emergent surgery, known cardiac dysfunction, renal dysfunction with serum Cr >1.0, hypertension necessitating intravenous hydralazine or labetalol during labor, and treatment with calcium channel blockers or digoxin.

Subject enrollment: All laboring patients on the unit receive a brief informational handout about this study upon admission (**Appendix 1**). Research staff visit all laboring patients twice daily after permission to approach and introduction by the bedside nurse, once in the morning and once in the afternoon, to obtain informed consent from all willing laboring patients if they require cesarean delivery. Consent and study inclusions/exclusions are confirmed by the clinical anesthesiologist at the time of decision by the obstetrics team to proceed with an intrapartum cesarean delivery.

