Subject exposures: Sequential subject study ID numbers will be randomized in 1:1 ratio to one of two experimental groups. Study drugs will be prepared daily by the research pharmacy and labeled only with the subject ID # and “study drug”. The patient, anesthesiologist, obstetricians, and research staff will remain blinded to assignment. All study subjects will receive standard care with prophylactic oxytocin bolus and infusion, as well as second-line uterotronics on an as-needed basis per institutional protocol. (**Appendix 2**)

- Calcium: 1 gram CaCl₂ in total volume 60mL delivered over 10 minutes beginning 2 minutes after fetal delivery.
- Placebo: 60mL sterile saline delivered over 10 minutes beginning 2 minutes after fetal delivery

Outcomes and Measurement: The primary outcome will be quantitative blood loss (QBL) in mL, which is calculated by standardized methodology including volumetric (suction cannister contents after subtracting amniotic fluid volume) and gravimetric (weighing soiled surgical sponges, drapes, and pads) assessment. Secondary outcomes will include the following: uterine tone assessments by the obstetric attending on a validated 10-point numerical rating scale¹⁴ (NRS_{UT}) at study drug initiation 2 minutes after fetal delivery and reassessed every 5 minutes thereafter until fascial closure. Additionally, total oxytocin bolus and infusion doses, second line uterotronics, change in hematocrit from preoperative to postoperative day one values, total intravenous fluids, and a composite outcome indicating hemorrhage morbidity including transfusion during the hospital stay, hysterectomy, uterine artery embolization, intensive care admission, and death will be recorded.

Please see Appendix 3 for forms to be filled out by research staff.

Data Analysis: Analyses will be conducted using R and supervised by a biostatistical consultant from the Stanford Quantitative Sciences unit. Continuous data will be represented using mean (\pm SD) or median (interquartile range) for variables not normally distributed and compared using parametric or non-parametric t-tests as appropriate. Categorical data will be presented using proportions and compared using a chi-square (or Fishers Exact) test. Two-sided p-values less than 0.05 will be considered statistically significant.

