Analysis of Primary Aim: The primary outcome of the study is the difference in quantitative blood loss between the two groups on an intention-to-treat basis. Patients who are found to have non-atomic reasons for blood loss including morbidly adherent placenta, hysterotomy extension, cervical, or vaginal lacerations will be included in primary outcome assessment. The trial is also powered for planned subgroup analysis excluding these cases. In addition, subgroup analyses based upon risk factors for atony including chorioamnionitis, total oxytocin exposure, indication for cesarean, magnesium infusion, and preeclampsia will be performed.

Sample size: Power analysis of the data from our pilot RCT revealed that a sample size of 31 patients per arm will have 90% power to detect a difference of 200mL in quantitative blood loss between groups at the $p<0.05$ significance level. The sample size was increased to 60 patients per arm to allow sufficient power for the planned subgroup analysis excluding patients with non-atomic etiologies of blood loss which may occur in up to 40% of cases. This same sample size will also generate 86% power to detect a rank test difference of 2 points in the ordinal secondary outcome measure of NRS_{UT} . We anticipate signing consent documents with approximately 1200 laboring patients to obtain the 120 subjects who meet enrollment criteria, as most of these patients will have normal spontaneous vaginal delivery, some may later decline to participate, some may develop exclusions such as renal dysfunction, and some may require stat delivery without time to safely administer the study medications in addition to standard care.

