Patient safety: All potential side effects of calcium will be recorded as part of this study, including flushing, arm discomfort, nausea, vomiting, bradycardia, tachycardia, arrhythmia, and hypertension. A single dose of dilute CaCl_2 , infused slowly through an intravenous (IV) line in the sensate upper extremity of an un-sedated patient, is unlikely to cause severe adverse effects. The major concern with CaCl_2 is tissue necrosis from extravasation. Any discomfort in the IV site will warrant immediate study drug infusion discontinuation with careful assessment of the extremity. The clinical anesthesiologist caring for the patient will also monitor for potential hemodynamic consequences of calcium infusion including bradycardia, hypotension, or hypertension. The anesthesiologist providing care to the patient will be instructed to assume the study drug contains 1 gram of CaCl_2 for all cases, and to immediately discontinue the infusion if they believe any the patient may be having a severe adverse effect. A data safety monitoring committee of two attending anesthesiologists with no involvement in the trial and with a track record of data safety monitoring has been created for this trial. Any potential adverse events including patient hemodynamic compromise or concern for drug extravasation will be reviewed immediately ad hoc, and they will determine whether unblinding is required and when the study may resume.

Management of hypercalcemia: Acute hypercalcemia may manifest as altered mental status, bradycardia, or hypotension. We do not anticipate clinical hypercalcemia given the patient population (young, healthy, renal dysfunction and digoxin use are contraindications), the dilute and slow infusion, the single dose of calcium, and the excellent patient tolerance and peak ionized calcium levels obtained during our pilot study. However, management of acute hypercalcemia would include immediately pausing the infusion if still running, administering a fluid bolus of 500mL to 1000mL isotonic fluid, and obtaining a serum calcium level at the discretion of the clinical anesthesia team. If necessary, the team could consider additional administration of 10-20mg intravenous furosemide to lower serum calcium further if needed.

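### The Appendix 3 eligibility checklist is looser than the protocol's criteria on age, gestational age and treated hypertension, so it passes patients whom the protocol excludes

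*Combined protocol and SAP*

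**What the plan says.** The Study population paragraph under Specific Aim 1 describes those to be enrolled as "adult pregnant patients age 18-45 years of age at >34 weeks gestation who require intrapartum cesarean delivery" and who have had exogenous oxytocin in labor. It excludes emergent surgery, known cardiac dysfunction, serum creatinine above 1.0, and "hypertension necessitating intravenous hydralazine or labetalol during labor, and treatment with calcium channel blockers or digoxin".

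Under Subject enrollment, "Consent and study inclusions/exclusions are confirmed by the clinical anesthesiologist at the time of decision" to proceed to cesarean. No tool for that confirmation is named.

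Outcomes and Measurement introduces the form: "Please see Appendix 3 for forms to be filled out by research staff". The first page of the Appendix 3 Protocol Sheet carries two blocks of boxes, one for inclusions and one to confirm that the patient has no exclusions. The syringe-pump instructions follow at once. The inclusion block asks about age (18 to 55), intrapartum cesarean, labor oxytocin and consent. The exclusion block asks about creatinine, cardiac conditions, calcium channel blockers, digoxin and emergencies.

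**The concern.** A sheet that asks staff to confirm the absence of exclusions tells its user that the list is complete. Here it is not, and one of its limits contradicts the protocol. For a 50-year-old, the form says eligible and the protocol says not, so the enrolled population is not clearly defined.

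The hypertension gap matters most, because that exclusion can arise after consent. Consent is sought in advance from about 1200 laboring patients to obtain 120 subjects, and the Sample size paragraph expects that "some may develop exclusions such as renal dysfunction". Intravenous treatment for hypertension during labor can likewise begin after consent is signed, so it has to be caught at a late check. Hypertensive patients are also foreseeable in this trial, since subgroup analyses by preeclampsia and magnesium infusion are planned. The Patient safety paragraph lists possible calcium effects "including flushing, arm discomfort, nausea, vomiting, bradycardia, tachycardia, arrhythmia, and hypertension", and it names hypertension again among the hemodynamic consequences to watch for.

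On the analysis side, the primary outcome is "the difference in quantitative blood loss between the two groups on an intention-to-treat basis". The plan gives no rule for randomized patients later found ineligible, so a patient dosed outside the criteria would presumably stay in the primary analysis.

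**Working it through.** No formula applies; the check is an item-by-item comparison. Calcium channel blockers and digoxin are counted separately, as the form does. The protocol body then has 4 inclusions and 6 exclusions, 10 criteria in all.

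| Criterion | Study population paragraph | Appendix 3 checklist | Result |
|---|---|---|---|
| Age | 18 to 45 | 18 to 55 | Looser on form |
| Gestation | Above 34 weeks | No box | Absent |
| Intrapartum cesarean | Required | Required | Consistent |
| Labor oxytocin | Required | Required | Consistent |
| Emergency | Emergent surgery excluded | Excluded where taking part could hinder or delay care | Reworded (qualified) |
| Cardiac | Known dysfunction | Any known condition | Reworded (stricter) |
| Renal | Creatinine above 1.0 | Creatinine above 1.0 mg/dL | Consistent |
| Hypertension treated with IV hydralazine or labetalol in labor | Excluded | No box | Absent |
| Calcium channel blocker | Excluded | Excluded, with a 24-hour window | Reworded (qualified) |
| Digoxin | Excluded | Excluded | Consistent |

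Tally: 2 absent + 1 looser + 3 reworded + 4 consistent = 10. Clearly permissive mismatches: 2 + 1 = 3. The form's exclusion block covers 5 of the 6 exclusions. The age window is 55 − 45 = 10 years wider, that is, ages 46 to 55.

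Three kinds of patient pass every box yet fail the protocol criteria:

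- one aged 46 to 55;
- one at 34 weeks or less;
- one given intravenous labetalol or hydralazine in labor for hypertension.

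The checklist reads continuously, with no gap or blacked-out item that could account for the missing boxes. On the form, hypertension appears only on the second page, as a possible side effect to record.

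The documents give no distribution of age, gestation or antihypertensive treatment, so the expected number of affected patients cannot be calculated. For scale only, one patient is 1/120 = 0.8% of the planned sample.

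**The case against.** The strongest reply is that passing the boxes is not the same as being dosed. The protocol makes the clinical anesthesiologist responsible for confirming inclusions and exclusions when cesarean is decided on. It does not limit that check to the form, which it describes as paperwork for research staff. Someone working from the protocol body would catch all three kinds of patient. This stands as a limit: the documents do not say that the form is the only check. There are, however, signs that it is the working one. It covers the same ground as the anesthesiologist's confirmation (consent, inclusions, exclusions). It repeats the instruction, given to the anesthesiologist under Patient safety, to assume that every syringe contains calcium. No other eligibility form appears.

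Several smaller objections also have force:

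- The late-exclusion argument applies to hypertension, not to age or gestation. The example the protocol gives of a late exclusion, renal dysfunction, is on the form.
- Recording hypertension as a side effect is a different task from screening for it, so its presence on the second page proves little.
- Retention under intention to treat is an inference. The protocol says "Sequential subject study ID numbers will be randomized in 1:1 ratio to one of two experimental groups", which suggests allocation ahead of enrollment, but it does not say when a patient counts as randomized.
- The 24-hour window and the qualified emergency wording could be read as looser too, so the count of three rests partly on classification. It is the conservative count.

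None of this removes the contradiction between the two lists.

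**Conclusion.** The concern holds. The checklist is more permissive than the protocol on three of ten criteria: two are missing and one has a limit ten years wider. A patient whom the protocol excludes can pass every box on the sheet that leads directly into dosing. Whether she would then be dosed depends on whether the anesthesiologist checks against the protocol body or against the form, and the documents do not settle this.

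The consequence is avoidable protocol deviations, a possible safety exposure through the hypertension omission, and an unclear definition of the enrolled population. How many patients would be affected is unknown. No bias between arms and no loss of power is claimed. The point should be fixed, but it does not undermine the design.

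**What to change.** Reconcile the Study population paragraph and Appendix 3 so that both carry one identical eligibility list. Every criterion the sponsor retains, including age, gestational age and the hypertension exclusion, should have its own box on the form. The cardiac, calcium-channel-blocker and emergency criteria should read the same in both places. Where the texts conflict, the sponsor must state which version is intended; the documents do not show it, and this review takes no position.

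The cost is a one-page form revision and an administrative amendment. Neither the sample size nor the analysis changes.

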- Patient received oxytocin infusion for labor induction or augmentation.
- Patient still wants to participate and has signed consents

Please confirm this patient has NO EXCLUSIONS:

- Patient does not have renal dysfunction with serum Cr>1.0 mg/dL
- Patient does not have any known cardiac conditions
- Patient is not receiving a calcium channel blocker (none in last 24 hours)
- Patient is not receiving digoxin for a maternal or fetal indication
- This is not an emergency in which participation in the study could hinder or delay care

Study drug:

- The syringe contains **60mL saline with 1-gram Calcium Chloride OR 60mL saline placebo**
- Administer via syringe pump and microbore tubing over 10 minutes
 - Program a basic infusion on Alaris pump for basic infusion, **360mL/hr**
 - Attach microbore tubing to injection port closest to the patient
 - Start infusion **2 minutes after fetal delivery** (1 minute after cord clamp)
- Assume that every infusion contains 1 gram of calcium and **discontinue** if concerns for extravasation (arm pain and redness or signs of infiltration), hemodynamic compromise (bradycardia and hypotension most common). Contact [name] via email or cell [contact] for any concerns and document on next page.

PLEASE FILL OUT ALL INFORMATION ON THE NEXT PAGE.

STUDY ID NUMBER (on study drug syringe): _____

USE EPIC COMPUTER CLOCK FOR ALL TIMES

Fetal Delivery and oxytocin 2 unit bolus :

Time: _____

2 minutes after fetal delivery:

• Ask obstetrician to rate uterine tone 0-10: Tone: _____

• Start study drug infusion: Time Started: _____

• *If infusion was paused or stopped* Time paused: _____

Time restarted: _____

7 minutes after fetal delivery:

• Ask obstetrician to rate uterine tone 0-10: Tone: _____

12 minutes after fetal delivery:

• Ask obstetrician to rate uterine tone 0-10: Tone: _____

19 minutes after fetal delivery:

• Ask obstetrician to rate uterine tone 0-10: Tone: _____

Side effects (did the patient experience any of the following possibly related to the study drug? Circle Yes/No)

- Arm or IV site discomfort? YES / NO
- Concern for extravasation? YES / NO
- Heart rate change or arrhythmia? YES / NO Describe: _____
- Hypertension or hypotension YES / NO Describe: _____
- Flushing YES / NO
- Abnormal sensations or tastes YES / NO Describe: _____
- Nausea YES / NO
- Vomiting YES / NO
- Other YES / NO Describe: _____

Was the infusion started exactly 2 minutes after fetal delivery? YES / NO

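### No uterine tone score or summary is named for the between-arm test, and the pre-drug 2-minute score is listed as an outcome rather than used as a baseline

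*Combined protocol and SAP*

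**What the plan says.** Under Specific Aim 1, Outcomes and Measurement, tone is a secondary outcome rated by the obstetric attending "at study drug initiation 2 minutes after fetal delivery and reassessed every 5 minutes thereafter until fascial closure". Subject exposures gives the active arm as "1 gram CaCl₂ in total volume 60mL delivered over 10 minutes beginning 2 minutes after fetal delivery", with placebo on the same timing. The Appendix 3 data form has four fixed entries: 2, 7 and 12 minutes, and then "19 minutes after fetal delivery". Under the 2-minute heading it asks for the score and then for the start of the infusion.

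Data Analysis gives generic two-group tests, parametric or not, for continuous data, and adds: "Two-sided p-values less than 0.05 will be considered statistically significant". For Aim 1 it states no baseline adjustment, repeated-measures method, summary score or multiplicity rule. Sample size claims "86% power to detect a rank test difference of 2 points in the ordinal secondary outcome measure", without a time point or a standard deviation (SD). Tone is the only secondary outcome named in the Aim 1 hypothesis and the only one given a power figure.

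**The concern.** The outcome is a series, while the power statement reads as one test of one value, and nothing connects the two. The first value in the series cannot show a drug effect because the infusion starts at that moment. Its natural use is as a baseline, but the plan lists it with the outcomes and gives it no other role in Aim 1.

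With the endpoint open, the analyst could test several scores and report the favourable one, or average across times and include the pre-drug score. The first inflates the false-positive rate. The second understates a true effect. Both bear on the claim, set out in the Aim 1 hypothesis, that calcium improves tone. The choice of time also changes what is measured: under Appendix 2 a score below 8 at 2 or 7 minutes leads to more oxytocin, so later scores reflect calcium plus score-driven co-treatment.

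**Working it through.** **Dose given at each score.** The form sets the pump at 360 mL/hr, which is 360/60 = 6 mL/min from minute 2.
- 2 min: 0 mL (fraction 0)
- 7 min: 5 × 6 = 30 mL (fraction 0.5)
- 12 min: 10 × 6 = 60 mL (fraction 1)
- 19 min: 60 mL (fraction 1)

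This assumes an on-time, uninterrupted infusion. The form records departures from that.

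**Schedule.** Scoring every five minutes from minute 2 gives 2, 7, 12, 17 and so on. The form's fourth entry is at 19, so the set of candidate scores is itself unsettled.

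**The plan's own power figure.** "The sample size was increased to 60 patients per arm", so n = 60. Power = Φ(δ / (SD × √(2/n)) − 1.96), with δ = 2.
- The pilot table gives interquartile ranges of 8–9 (calcium) and 7–9 (placebo), one tone value per patient with no time stated. Dividing the widths by 1.349 (normal shape assumed) gives SDs of 0.74 and 1.48, pooled 1.17.
- With any of these, power for 2 points exceeds 99.9%. At SD 1.48: 2 / (1.48 × 0.1826) = 7.4, far above 1.96.
- To obtain 86%, SD = 2 / ((1.960 + 1.080) × 0.1826) = 3.60. A rank-test efficiency factor of 3/π lowers this to 3.52.

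The 86% was therefore not reproduced. That does not show it is wrong, because its SD, distribution and time point are not given, and the pilot SDs assume normality on a bounded scale.

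**If each post-start score were tested at 0.05.** The form has three (7, 12 and 19 min). If they were independent, 1 − 0.95³ = 14.3%. For normal test statistics with a common correlation (assumed), the chance of at least one |z| > 1.96 with no true effect is:

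| Correlation | 3 tests |
|---|---|
| 0.3 | 13.6% |
| 0.5 | 12.5% |
| 0.7 | 10.9% |
| 0.9 | 8.4% |

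**If all four form scores were averaged.** Assuming effect follows dose given, the share of the full effect is (0 + 0.5 + 1 + 1)/4 = 0.625, so 2 points becomes 1.25. Averaging also lowers the variance: SD of the mean = SD × √((1 + 3ρ)/4). With SD 3.60 and ρ = 0.5, this is 3.60 × 0.791 = 2.85. Then 1.25 / (2.85 × 0.1826) = 2.40 and power is Φ(0.44) = 67%, against 86% for one fully exposed score. The range is 79% at ρ = 0.3 to 51% at ρ = 0.9. With SD 1.48 the loss is negligible: even at ρ = 0.9, 1.25 / (1.48 × 0.962 × 0.1826) = 4.8, power above 99%. The understated effect remains either way.

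**What baseline adjustment could gain.** In a linear approximation, adjusting for the 2-minute score multiplies the residual variance by 1 − ρ². On the scale where one unadjusted score has 86% power, power becomes Φ(3.040/√(1 − ρ²) − 1.96):
- ρ = 0.3: Φ(1.23) = 89%
- ρ = 0.5: Φ(1.55) = 94%
- ρ = 0.7: Φ(2.30) = 99%

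**The case against.** The strongest reply is that a measurement schedule is not a list of tests. The protocol labels the 2-minute score as taken at drug initiation, so its status is visible. Appendix 2 records it in routine care, and the Aim 2 effect-site model needs serial scores to estimate baseline probability and delay. The power statement describes one rank test. All of this is correct. Collecting the 2-minute score is not a flaw, and Aim 2 gives the series a purpose. None of it says what Aim 1 compares between arms.

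A reader might infer that the plan both blends pre-drug scores into the test and repeats that test at 0.05. The documents support neither. Pooling and repeated testing are alternative outcomes of an open choice.

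A reader might also infer that the 7-minute score precedes any effect. Half the dose is in by then, and the protocol leaves any delay to be modelled, so it is a mid-infusion score and no more can be said.

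An average of 2, 7 and 12 minutes alone would show half the effect, but that leaves out the form's 19-minute entry.

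It can fairly be argued that 12 minutes is not plainly the best time. Extra oxytocin may already have been given, and a delayed effect could peak later. That stands, so the fix does not insist on it.

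**Conclusion.** The point holds as a gap with a cheap remedy. The plan lists a pre-treatment score among its tone outcomes, names no score or summary for the between-arm comparison, and offers only an unadjusted test at two-sided 0.05.

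If the three post-start form scores were each tested, the chance of at least one false positive would be about 11% to 14%, resting on assumed correlations of 0.7 to 0.3. If all four scores were averaged, about 0.625 of the full effect would show, resting on the assumption that effect follows dose given. The accompanying fall in power from 86% to about 67% also needs an SD near 3.60, far above what the pilot suggests, so it should not be read as a forecast.

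The conclusion on quantitative blood loss is not touched. The matter deserves correction because tone carries its own hypothesis and power claim in Aim 1.

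**What to change.** Before unblinding, amend the analysis text as follows.
1. Define the 2-minute score as the baseline and remove it from the outcomes.
2. Name one post-infusion tone endpoint, for example the 12-minute score or the mean of the 12 and 19 minute scores.
3. Compare arms once on that endpoint, adjusting for the 2-minute score. Ordinal regression suits a single score.
4. Report all other scores descriptively, with oxytocin dose and second-line uterotonic use by arm beside them.
5. Reconcile the five-minute schedule in Outcomes and Measurement with the form's 19-minute entry.
6. Recompute the tone power for the named endpoint and state the SD and its source. Do not simply carry the 86% over.

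The cost is wording and one power calculation. The form already collects the four scores, and no patients or procedures are added. There are two small downsides: a single endpoint may miss an effect at other times, and score-triggered oxytocin may shrink the difference seen at later scores.
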